3.2.3 Documentation

Data including baseline clinical and procedural characteristics with all FFR values (pre- and post-PCI resting, dPR, contrast, and adenosine) will be entered into the electronic case report form (eCRF) and used to analyze the primary and secondary study endpoints. These data will be stored in the IBM Clinical Data platform mirroring the NCDR dataset.

The post-PCI (final) aFFR will be used for correlation to 1-year clinical outcomes of death, MI, and TVR. These clinical endpoints will be recorded during the index hospitalization (prior to discharge), 30-day visit (at the routine follow-up appointment or telephone call if this appointment is missed), and at 1 year by telephone. See post-procedure follow-up section for details on data acquisition and definitions.

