 - iv. Inject contrast to fill guide catheter and wait for return of baseline hemodynamics.
 - v. Press record on ACIST FFR console and then inject contrast at standard settings above for cFFR. Within the first minute of contrast injection, the nadir cFFR value will be logged.
 - vi. The recorded tracings will be captured and saved for an independent FFR core lab review.
- d. Adenosine FFR (aFFR)
 - i. Return of baseline hemodynamics
 - ii. Intravenous adenosine administered at a rate of 140 µg/kg of body weight per minute x 2 minutes will then be performed and the aFFR value logged.
 - iii. If the aFFR is >0.80, then no PCI is performed and this final FFR value will be logged for correlation to long-term outcomes.
 - iv. If the aFFR is ≤0.80, then PCI according to standard techniques will be performed. Post-PCI, the NAVVUS FFR microcatheter will be used to measure resting Pd/Pa, dPR, contrast FFR, and adenosine FFR in the same manner as above with values recorded.
 - v. The recorded tracings will be captured and saved for an independent FFR core lab review.

5. Drift

- a. Drift check will be performed at least once during each procedure and ideally after each use/measurement of the NAVVUS FFR microcatheter
- b. Clinically significant drift will be defined as $> \pm 0.03$ (12).
- c. The presence of any significant drift (yes/no) will be recorded. If there is clinically significant drift, the FFR measurements will be repeated after repositioning of the guide catheter and re-equalization.

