12.2 Fractional Flow Reserve Core Lab

This purpose of the core lab will be to review the quality and validity of each FFR tracing obtained from all subjects enrolled in the study as well as derive the dPR via waveform analysis. The core lab will consist of 1 physician knowledgeable in FFR physiology and the catheter techniques employed for proper FFR acquisition and 1 engineer from the ACIST team with specific knowledge about FFR acquisition and data analysis from the NAVVUS RxI FFR system. These 2 members will perform an independent, blinded review of all FFR tracings and will make a recommendation for exclusion if any of the following criteria are noted: ventricularization of aortic waveform, change in dampening/distortion of aortic waveform, or significant signal drift. Discrepancies in recommendations will be resolved by joint review of the 2 members of the tracing in question.

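### The primary analysis takes cFFR and aFFR as logged during the procedure, with no aFFR reading rule and no described masking, although a core lab already reviews every saved tracing and could supply both values.

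*Combined protocol and SAP*

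**What the plan says.** Section 3.2.3 (Documentation) lists all FFR values, contrast and adenosine included, and says they "will be entered into the electronic case report form (eCRF) and used to analyze the primary and secondary study endpoints". Section 9 names no other source for the analysed values.

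Section 3.2.2, step 4, fixes the order of measurement. For contrast: "Within the first minute of contrast injection, the nadir cFFR value will be logged". After return to baseline, the adenosine infusion "will then be performed and the aFFR value logged". No nadir, steady-state or time-window rule is given for aFFR. The aFFR result is acted on at once: "If the aFFR is ≤0.80, then PCI according to standard techniques will be performed". For both methods: "The recorded tracings will be captured and saved for an independent FFR core lab review".

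Section 12.2 gives the core lab the task to "review the quality and validity of each FFR tracing obtained from all subjects enrolled in the study as well as derive the dPR" from the waveforms. It adds: "These 2 members will perform an independent, blinded review of all FFR tracings and will make a recommendation for exclusion". The outputs named are quality review, exclusion recommendations and dPR. Numeric cFFR and aFFR readings are not among them. One of the two core-lab members is a physician and the other is an engineer from the device company.

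**The concern.** This is a method comparison, so how the two numbers are read is part of the endpoint. The rationale in section 1 is that earlier work did not standardise contrast injection. The plan standardises the injection and the reading of the index test, but not the reading of the reference standard.

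Three mechanisms follow, and they do not act in the same direction:

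- **Carry-over.** If whoever logs aFFR has seen cFFR, borderline aFFR values may be settled on the side that cFFR suggests. That raises the AUC.
- **Inconsistent reading.** If different people pick different points on the adenosine tracing, random error enters the reference classification. That lowers the AUC.
- **A systematic difference.** If aFFR is read consistently higher or lower than intended, the estimated bias moves. So does the cFFR cutoff, because section 9.3.2 derives it from the fitted model at aFFR 0.80.

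At stake are the false-positive rate and power of the AUC test and the location of the derived cutoff.

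**Working it through.** **1. The plan's sample size.** Inputs from section 9.3.2: null AUC 0.80, alternative 0.90, ratio of negatives to positives k = 1.06, SD ratio 1, two-sided alpha 0.05, power 0.90. With the usual binormal approximation,

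V(A) = 0.0099 · exp(−a²/2) · [(5a² + 8) + (a² + 8)/k], where a = 1.414 · Φ⁻¹(A).

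This gives V(0.80) = 0.1169 and V(0.90) = 0.0672. Then

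n_pos = (1.960·√0.1169 + 1.282·√0.0672)² / 0.10² = 100.5, rounded up to 101.

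n_neg = 1.06 × 101 = 107, and the total is 208, as stated. The sample size is not in dispute, and the fix leaves it unchanged.

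**2. Assumptions for the illustration.** The documents give no reading-error data. Assumed: aFFR normal with SD 0.08-0.10; 1/2.06 = 48.5% of lesions at or below 0.80 (from the plan's ratio); cFFR = aFFR + 0.03 + noise. The 0.03 is the gap between the 0.80 and 0.83 cutoffs. The noise is set to give a true AUC of 0.80 or 0.90 (at SD 0.09, about 0.107 and 0.060).

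**3. Carry-over, true AUC 0.80.** Suppose a share of the lesions with aFFR within 0.02 of 0.80 is logged on the side given by cFFR ≤0.83. For shares of 10% to 50%, the apparent AUC by simulation is about 0.806 to 0.837. The chance of rejecting the null with 208 pairs is

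Φ{[(A − 0.80)·√(208/2.06) − 1.960·√V(0.80)] / √V(A)}.

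| Share (SD 0.09) | Apparent AUC | Chance of rejecting |
|---|---|---|
| 0% | 0.800 | 2.5% |
| 10% | 0.807 | about 4% |
| 25% | 0.816 | about 6% |
| 50% | 0.833 | about 15% |

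**4. Inconsistent reading, true AUC 0.90.** Random aFFR reading error of SD 0.02 lowers the AUC to about 0.886 (SD 0.08) to 0.891 (SD 0.10). The same formula gives:

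- A = 0.886: V = 0.0760, (0.864 − 0.670)/0.276 = 0.70, power about 76%.
- A = 0.891: V = 0.0729, (0.914 − 0.670)/0.270 = 0.905, power about 82%.

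The plan intends 90%.

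**5. Uniform shift in aFFR.** With aFFR centred on 0.80, a shift d reclassifies Φ(d/SD) − 0.5 of lesions. That is 4.0% at d = 0.01, SD 0.10, and 9.9% at d = 0.02, SD 0.08. Yet in simulation, shifting every aFFR by ±0.01 or ±0.02 moves the AUC by only about 0.002. The effect falls elsewhere. If every aFFR is read d too low, then with unit slope cFFR = read aFFR + 0.03 + d, so the estimated bias and the cutoff both move by d. At d = 0.02 the cutoff becomes 0.85 instead of 0.83, a move of two-thirds of the expected 0.03 gap.

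**The case against.** Several stronger readings are tempting, and the documents do not support them.

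- **That unblinded operators are documented as reading both tests.** Section 3.2.2 uses the passive and does not say who logs. That this person has seen cFFR is an inference from the fixed order, the absence of any masking step and aFFR deciding PCI on the spot. It is a reasonable inference, but it is not a stated design.
- **That every eCRF value is a site reading.** The eCRF list includes dPR, which the core lab derives, so the eCRF alone does not prove the source. For cFFR and aFFR, however, section 3.2.2 has them logged in the procedure and no section assigns their reading to the core lab.
- **That agreement is biased upward.** This holds for carry-over only. Inconsistent reading works the other way, and the net direction is unknown.
- **That 4%-10% reclassification threatens the AUC test.** That figure comes from a uniform shift, which hardly touches the AUC.
- **That the core lab's blinding already solves the problem.** Section 12.2 does not say what the readers are blinded to. It need not mean that cFFR and aFFR tracings are masked from each other.

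It is also fair to say that the console may compute the values, which would leave less to judgement. The documents do not say so, and even then the aFFR window and the choice to repeat a run would stay open. Nor must the two rules be identical: one method follows a bolus and the other an infusion. What is missing is a rule for aFFR. Finally, moving the values to the core lab gives a device-company employee a part in reading both tests, which the fix has to handle.

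**Conclusion.** The point stands in this form. The primary endpoint rests on values logged in the procedure, the reference standard has no reading rule, no masking is described, and a better source is already in place but is not used for these two numbers. A reader might infer a demonstrated upward bias from unblinded operators; the text supports neither the label as fact nor the fixed direction.

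The true size cannot be known from the documents. The illustrations rest on an assumed aFFR SD, an assumed model for cFFR and assumed amounts of reading error. Within them, carry-over at a true AUC of 0.80 takes false rejection from 2.5% to between 4% and 15%, and reading error of SD 0.02 at a true AUC of 0.90 takes power from 90% to between 76% and 82%. A systematic difference matters for the bias estimate and the cutoff, not for the test. This should be corrected before the analysis; it does not make the design unworkable.

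**What to change.** State in sections 3.2.3, 9.3 and 12.2 that the primary analysis uses core-lab cFFR and aFFR values read from the saved tracings, and specify:

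1. A pre-specified reading rule for each method. The cFFR rule exists and the aFFR rule must be added; the two need not match.
2. De-identified cFFR and aFFR tracings, read separately and masked to each other and to the logged values.
3. How numeric disagreement is resolved. The joint review in section 12.2 covers exclusion recommendations only. Because one reader is from the device company, either make the physician's reading the value of record or set a resolution rule in advance.
4. The procedure-logged values as a sensitivity analysis. They continue to guide care, so nothing changes in the catheterization laboratory.

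The cost is two more recorded values per assessment for readers who already open every tracing. The sample size stays at 208 pairs, and saved tracings can be re-read at any time before the analysis. Central reading does not remove any effect of the fixed cFFR-then-aFFR order on the measurements themselves, and the report should say so.

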3.3 Endpoints

3.3.1 Primary Endpoint

The primary endpoint of the study is the accuracy and correlation of cFFR in comparison to aFFR, where cFFR is performed using the ACIST CVi automated contrast injector with a standardized volume and rate of delivery of contrast with known osmolality.

3.3.2 Secondary Endpoints

The secondary endpoint is the association between the final post-PCI aFFR and long-term clinical outcomes. The long-term clinical outcomes will include TVR and composite MACE (death, MI, and TVR) during the index hospitalization, 30 days, and 1 year.

4. SELECTION AND WITHDRAW OF PATIENTS

Up to 200 patients \geq 18 years of age who are eligible for non-emergent PCI will be enrolled.

4.1 Clinical Inclusion Criteria

To be eligible for enrollment, subjects must meet all the following criteria:

1. Have the capacity to understand and sign an informed consent or have a legally authorized representative (LAR) that can understand and sign an informed consent prior to initial arteriotomy access
2. Age \geq 18 years of age at the time of signing the informed consent
3. Clinically stable and undergoing non-emergent cardiac catheterization for appropriate indications
4. Willing to be contacted by telephone at 30 days (if no standard of care visit) and at 1 year with chart review for events.

4.2 Clinical Exclusion Criteria

If a subject meets any of the following criteria, he or she will not be consented:

1. Any condition associated with a life expectancy of less than 1 year
2. Participation in another clinical study using an investigational agent or device within the past 3 months
3. Ejection fraction \leq 35%
4. Creatinine \geq 2
5. Severe valvular heart disease
6. Decompensated acute diastolic or systolic heart failure
7. Bronchospastic chronic obstructive pulmonary disease or other intolerance to adenosine

4.3 Angiographic Inclusion/Exclusion Criteria

After the diagnostic angiography, patients having an intermediate lesion(s) meeting the following angiographic criteria will be enrolled:

Inclusion:

Target vessel with an intermediate lesion of 40-70% stenosis by angiographic assessment (a visual estimation by the operator). Serial lesions, diffuse disease, or ostial lesions ("all-comer" lesions) are acceptable if the operator would normally perform FFR and proceed with PCI (or other revascularization) if positive.

Exclusion:

1. ST-segment elevation myocardial infarction culprit lesion or lesions with any thrombus burden

2. Lesions with severe calcification
3. Lesions in a target vessel supplied by a patent graft

4.4 Withdrawal of Patients

Patients may voluntarily withdraw for any reason without penalty or loss of benefits to which they are entitled.

If a patient withdraws from the study at any time either at his or her request or at the investigator's discretion, the reasons for withdrawal must be recorded on the relevant page of the patient's eCRF. Patients who withdraw from the study prematurely should undergo all end-of-study assessments, if possible. Study site personnel should make every effort to prevent losing patients to follow-up.

5. KNOWN AND POTENTIAL RISKS

The risks of FFR assessment in stable CAD are well described in large-scale randomized controlled trials (1, 2). These risks are generally considered to be low and acceptable, even in the setting of multivessel disease (1, 2), acute coronary syndromes (13, 14), and serial lesions (15). Based on low risk, high value in characterizing lesion significance, and improving clinical outcomes, FFR has been incorporated into multi-society supported Guidelines and Appropriate Use Criteria for coronary revascularization (3-6).

The goal of this study is to compare two different methods of acquiring FFR – contrast FFR to the gold-standard adenosine FFR. Contrast FFR is potentially a safer approach to FFR. Contrast FFR has been previously studied and compared with aFFR; however, there has been variability in the type, volume, and rate of contrast injected to induce vessel hyperemia with a manual (manifold) injection setup. Standardizing the injection with the ACIST CVi automated contrast injector may mitigate the variability for induction of hyperemia and provide a more robust comparator to systemic adenosine. The risk of contrast-induced nephropathy in contrast FFR is expected to be neutral compared with aFFR, since approximately the same amount of contrast would be injected during cFFR for hyperemia induction as would be delivered during the wiring and verification of wire position steps for traditional pressure wire FFR with adenosine. To mitigate risk, only patients without renal insufficiency will be enrolled. Furthermore, use of the ACIST automated injector is known to be associated with a significant reduction in the total volume of contrast media used and in the net amount of contrast delivered to patients when compared with traditional methods of manual (manifold) contrast injection (16). This pattern held true across varying types of procedures—97.4%, 53.8%, and 57.3% more contrast media was used during manual injection compared with the ACIST automated contrast injector for diagnostic, diagnostic with PCI, and PCI alone procedures, respectively (16).

This protocol will use the FDA-cleared NAVVUS RXi microcatheter for FFR assessment, which comes with several advantages that would render the assessment and management of all-comer intermediate lesions safer and with greater success, even in tortuous vessels. For example, the operator can choose any standard workhorse coronary guidewire for initial wiring. In addition, the unique design of the fiber-optic pressure sensor near the tip of a monorail microcatheter allows for ease of traversing forward and backwards over the standard 0.014" coronary guidewire without losing wire position. In the CONTRACT study evaluating over 200 patients randomized to either NAVVUS (n=87) or pressure wire (n=141), the NAVVUS catheter had a high lesion crossing success rate (96.9%) and was safe (17). There were no differences between the 2 groups with respect to contrast or radiation dose.

In the current study, there is the possibility of requiring multiple FFR recordings per vessel. Each run will include a repeat dose of systemic adenosine (risk of known patient side effects from adenosine), contrast (risk of contrast-induced nephropathy), time on anticoagulation (risk of bleeding), and radiation exposure (risk of skin injury). We will mitigate these risks by including patients with no contraindications to adenosine, normal baseline renal function, careful monitoring of ACT while on procedural anticoagulation, and safe radiation practices, such as using radiation filters and changing camera

angulation. We do not anticipate any additional safety concerns, as multiple FFR acquisitions per patient has already been shown to be safe in the setting of multivessel disease. In fact, in the initial FAME trial of multivessel disease, the number of indicated lesions undergoing FFR assessment with systemic IV adenosine was 2.8, yet this arm was found to have improved clinical outcomes compared with the angiography-guided PCI arm (1). Multiple studies have also demonstrated the value of measuring post-PCI FFR in clinical practice, as there is strong correlation to long-term outcomes (10, 11).

Our study sites will only include centers that currently use the ACIST contrast injector and NAVVUS FFR microcatheter in routine clinical practice. Familiarity with these devices will assist in mitigating risk. Furthermore, most operators in our study perform diagnostic and coronary interventions via radial access, a method known to reduce bleeding risk, which will mitigate the risks of procedural anticoagulation.

As with any clinical investigation, study records that identify subjects will be kept confidential as required by law. Information systems used to maintain study records will comply with federal privacy regulations and safeguards for privacy, security, and authorized access. Informed consent will be obtained. Subjects will be assigned a unique code number to identify their records for other study-related activities.

As part of the study, sites will report the results of study-related tests and images to the DCRI. These would include cardiac catheterization reports and FFR tracings for review by an independent FFR core lab. Risks will be further minimized by appropriate review by the individual site IRBs.

6.1 Screening Procedures

Potentially eligible subjects will be screened upon confirmation of non-emergent PCI. Study personnel will assess each subject against study inclusion and exclusion criteria, and the investigator will determine the subject's eligibility for participation.

6.2 Informed Consent

Each site will submit the study protocol, informed consent form (ICF), and other study documents to their ethics committee IRB for approval. A copy of the signed and dated IRB approval for each enrolling center will be stored at the Data Coordinating Center (DCRI). Any amendments to the protocol, other than minor administrative changes, must be approved by the site's IRB before the changes are implemented at the site.

The informed consent process will be documented in the subject's medical record or comparable source document.

Consent will be obtained from the subject or their LAR prior to arterial access and, if the subject is consenting, prior to the administration of any medications that might affect patient cognition.

6.3 Enrollment

Once a subject has met all clinical inclusion/exclusion criteria and provided informed consent, the subject will be eligible for study enrollment. Study staff is encouraged to appropriately identify candidates consistent with study objectives.

After the diagnostic angiogram, subjects who meet angiographic criteria of any intermediate lesion(s) as defined by the protocol will be enrolled.

6.4 Screen Failures

All subjects who are consented but not enrolled due to angiographic inclusion and exclusion criteria will be logged in the eCRF as a screen failure.

6.5 Post-procedure Follow-up

Subjects will be seen for their standard post-procedure visit (approximately 30 days post-procedure). Additional follow-up will be completed at 1 year via telephone call. Subjects will be asked to report indications for any hospitalizations, cardiac catheterization procedures, and/or coronary interventions since the index enrollment procedure. Subjects will be asked specifically about clinical events including MI and revascularization with further stents. Source documents will be collected and reviewed to verify clinical endpoints.

6.6 Schedule of Events

The schedule of study assessments and procedures is provided in Table 1:

Table 1 Schedule of Assessments

	Screening and Pre-enrollment	Enrollment /Procedure	Post-procedure	30 (± 7) Days	1 Year (± 30 Days)
Inclusion/exclusion criteria - enrollment	X				
Informed consent and patient contact form details	X				
Medical history	X			X	X
Physical assessment, vital signs (standard of care)	X ^a			X	
Concomitant medications	X ^a			X	X
Diagnostic angiogram	X				
Coagulation labs		X ^b			
Perform resting, dPR, contrast, and adenosine FFR		X			
Perform post-PCI FFR if applicable		X			
Collection of specified CV endpoints (death, MI, TVR)			X ^c	X ^c	X ^c

FFR, fractional flow reserves; dPR, diastolic Pressure Ratio; PCI, percutaneous coronary intervention; MI, myocardial infarction; TVR, target vessel revascularization

^a Within 7 days or immediately before enrollment .

^b confirm anticoagulation prior to coronary wire exiting the guide catheter

^c All serious adverse events related to the NAVVUS RxI FFR microcatheter system. Specified cardiovascular endpoint events data collection will be reported on the eCRF endpoint pages only

7. DATA CAPTURE

An electronic data capture (EDC) system will be used for this study (IBM Clinical Data/eCOS). All users will be trained on the technical features of the EDC as well as the content of the eCRF by qualified personnel prior to gaining access to the EDC. A user ID/password will be granted after training. This ID is not to be shared amongst the study staff. All users must have a unique account to enter or review data. The eCRF should be filled out by the site 3 days after each visit. It is not expected that the eCRF will serve as source for any data collected in this study. If there is a reason for a site to do so, it must be approved by and documented in the site files.

Prior to the database being locked, the investigator or designee will review, approve, and sign/date each completed eCRF. This signature serves as attestation of the investigator's responsibility for ensuring that all data entered into the eCRF are complete, accurate, and authentic.

